11.1.3. Health-Related Quality of Life

Health-Related Quality of Life, as assessed by the SAT, SAC BDI-TDI, KSQ, LCQ, and FAS. Scores and change from baseline for each questionnaire are summarized and listed using the mITT and EE Set.

For the change from baseline for each subscore or total score below, individual/combined active treatment arm will be compared to placebo using the pseudo code below. The integer scores are treated as continuous. Restricted maximum likelihood and Kenward Rogers (1997) method for degrees-of-freedom will be used.

```
proc mixed data = score method=reml;
  class trt01p(ref='Placebo') avisit usubjid;
  model change_from_baseline = trt01p avisit trt01p*avisit base / ddfm=kr;
  repeated / subject=usubjid type=un;
  lsmeans trt01p*avisit /pdiff=all cl;
run;
```

11.1.3.1. Sarcoidosis Assessment Tool (SAT)

The SAT is a sarcoidosis-specific patient-reported outcome developed for use in sarcoidosis clinical studies to measure the patient's assessment of impact of disease and response to therapy. It utilizes Item Response Theory to allow the use of a short questionnaire.

The questionnaire contains 8 subscales:

1. Physical Functioning (daily activities) (6 Questions)
2. Satisfaction with Roles and Activities (5 Questions)

aTyr Pharma, Inc.
Study ATYR1923-C-002 Statistical Analysis Plan
IND#: 133692

FINAL Version 1.0
2021-08-02

3. Pain Interference (5 Questions)
4. Sleep Disturbance (5 Questions)
5. Fatigue (5 Questions)
6. Sarcoidosis-Lung Concerns (10 Questions)
7. Sarcoidosis-Skin Concerns (10 Questions)
8. Sarcoidosis-Stigma (embarrassment) (5 Questions)

The scoring of this questionnaire is done via a SAS macro provided by Victorson *et al* (2013).

Each instance of a subscale needs to contain at least 4 valid responses in order to be scored. Subscale scores will be rounded to the first decimal place. All subscale scores and change from baseline will be summarized by treatment and listed. No total score will be calculated.

This tool is currently experimental, and the results will also be treated as exploratory.

11.1.3.2. The Self-Administered Computerized Baseline and Transitional Dyspnea Indices (SAC BDI-TDI)

The BDI measures the severity of dyspnea at the baseline (or the beginning of a clinical study), and the TDI measures changes from this baseline (transition period) at subsequent visits. The BDI and TDI each contain 3 domains including functional impairment, magnitude of task, and magnitude of effort. The lower the score on the BDI, the worse the severity of dyspnea at baseline and the lower the score on the TDI, the more deterioration in the severity of dyspnea. The minimal clinically important difference of the TDI is a total score of 1.

The BDI is administered on Day 1, while the TDI is administered at Weeks 4, 8, 12, 16, 20 and 24/Early Termination visits.

The total score for BDI will be the summation of all 3 domains. TDI total scores are the summation of all 3 domains divided by 2. If any individual item is missing, then the total score is missing. If the BDI for a subject is missing, the TDI can still be included in analyses. BDI and TDI domains and total scores will be summarized separately by visit and treatment. Individual items for BDI and TDI will be listed together.

11.1.3.3. King's Sarcoidosis Questionnaire (KSQ)

The KSQ is a 29-item questionnaire to be completed by patients, with 5 domains:

1. General health status (GHS),
2. Lungs,
3. Medication,

4. Skin, and
5. Eyes.

The KSQ is administered on Day 1 and Weeks 4, 8, 12, 16, 20 and 24/Early Termination Visits. All 5 domains and the GHS-Lung score, scored using logit scores with each logit score ranging from 0 and 100 (except the GHS-Lung score which is the sum of the GHS and Lungs scores and ranges from 0 to 200), and change from baseline will be summarized by visit and treatment. The domains and the GHS-Lung score will be listed. See Appendix 1: King's Sarcoidosis Questionnaire (KSQ) scoring information for further details on KSQ scoring.

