APPENDIX 1: KING'S SARCOIDOSIS QUESTIONNAIRE (KSQ) SCORING INFORMATION

Calculating the logit scores in KSQ as obtained directly from vendor.

Notes

1. Example below is for the General Health Status domain. Use the same principle for other domains and combinations of domains.
2. The most useful scores are the 5 domain scores GHS, Lung, Skin, Eyes and Medications. Combination of domain scores are possible but usually not necessary (GHS-Lung is best when a single combined score is required rather than individual domain scores).
3. If more than 50% of the answer of a given module is missing, then the module score is considered missing. Combined score of multiple modules is then also considered missing.
4. If 50% or fewer of the questions have missing or invalid results, then the missing scores are replaced with module averages in the original score before re-score.

Step 1: Check the raw item responses as completed by the patient

Quality of life-QOL Domain (General health status)

	In the last 2 weeks...	All of the time	Most of the time	A good bit of the time	Some of the time	A little of the time	Hardly any of the time	None of the time
1	I have felt frustrated	1	2	3	4	5	6	7
2	I have had trouble concentrating	1	2	3	4	5	6	7
3	I have lacked motivation	1	2	3	4	5	6	7
4	I have felt tired	1	2	3	4	5	6	7
5	I have felt anxious	1	2	3	4	5	6	7
6	I have felt aches and pains in my muscles/joints	1	2	3	4	5	6	7
7	I have felt embarrassed	1	2	3	4	5	6	7
8	I have worried about my weight	1	2	3	4	5	6	7
9	I have worried about my sarcoidosis	1	2	3	4	5	6	7

aTyr Pharma, Inc.
 Study ATYR1923-C-002 Statistical Analysis Plan
 IND#: 133692

FINAL Version 1.0
 2021-08-02

	In the last 2 weeks...	A huge amount	Considerable amount	A moderate amount	A Modest amount	A small amount	A tiny amount	None at all
10	Tiredness has interfered with my normal social activities such as going out with friends/family	1	2	3	4	5	6	7

Step 2: Convert these raw individual scores into the re-scores using the Recoding Matrix.

For example, as patient responded to item 1 with “4”, look up rescore value in QOL TAB. This score now is converted to “3.” See screenshot below.

	A	B	C	D	E	F	G	H	I	J	K
1	Item	Max Score	Rescored	1	2	3	4	5	6	7	
2	I0001	4	Y	0	1	2	3	3	4	4	
3	I0002	6		0	1	2	3	4	5	6	
4	I0003	3	Y	0	1	1	2	2	3	3	
5	I0004	6		0	1	2	3	4	5	6	
6	I0005	3	Y	0	1	2	2	3	3	3	
7	I0006	2	Y	0	0	1	1	1	2	2	
8	I0007	3	Y	0	0	0	1	2	2	3	
9	I0008	2	Y	0	0	1	1	1	2	2	
10	I0009	2	Y	0	0	1	1	1	2	2	
11	I0010	2	Y	0	0	1	1	1	2	2	

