12											
13		33									
14											
15											

Therefore, re-score total is 20.

Step 3: Convert the re-score total into the logit 0-100 scale by using the logit conversion list and looking up the appropriate domain, e.g. GHS.

	G	H	I	J	K	L	M	N	O	P	Q	R	S	T	U	V	W	X	Y
1		EYE				MEDS			LUNG				GHS				GHS L		
2	-3.646	0.0			0	-2.506	0.0		0	-3.817	0.0		0	-4.283	0.0		0	-4.927	0.0
3	-2.803	11.3			1	-1.76	14.5		1	-2.975	10.4		1	-3.491	9.3		1	-3.875	11.6
4	-2.18	19.6			2	-1.13	26.8		2	-2.402	17.5		2	-2.941	15.7		2	-3.201	19.0
5	-1.719	25.8			3	-0.594	37.2		3	-2.012	22.3		3	-2.558	20.2		3	-2.769	23.8
6	-1.333	31.0			4	-0.094	47.0		4	-1.715	26.0		4	-2.256	23.8		4	-2.459	27.2
7	-0.992	35.5			5	0.395	56.5		5	-1.475	29.0		5	-2.002	26.7		5	-2.22	29.9
8	-0.68	39.7			6	0.929	66.9		6	-1.274	31.4		6	-1.778	29.4		6	-2.026	32.0
9	-0.392	43.5			7	1.649	80.9		7	-1.1	33.6		7	-1.576	31.7		7	-1.863	33.8
10	-0.122	47.2			8	2.627	100.0		8	-0.947	35.5		8	-1.389	33.9		8	-1.722	35.4
11	0.137	50.6							9	-0.808	37.2		9	-1.213	36.0		9	-1.598	36.7
12	0.391	54.0							10	-0.681	38.8		10	-1.046	38.0		10	-1.487	38.0
13	0.649	57.5							11	-0.562	40.2		11	-0.884	39.9		11	-1.386	39.1
14	0.922	61.1							12	-0.45	41.6		12	-0.726	41.7		12	-1.294	40.1
15	1.226	65.2							13	-0.343	42.9		13	-0.57	43.5		13	-1.208	41.0
16	1.589	70.1							14	-0.239	44.2		14	-0.416	45.3		14	-1.128	41.9
17	2.062	76.4							15	-0.139	45.5		15	-0.264	47.1		15	-1.052	42.8
18	2.769	85.8							16	-0.04	46.7		16	-0.111	48.9		16	-0.981	43.5
19	3.827	100.0							17	0.056	47.9		17	0.042	50.7		17	-0.912	44.3
20									18	0.151	49.1		18	0.196	52.5		18	-0.847	45.0
21									19	0.246	50.2		19	0.351	54.3		19	-0.784	45.7
22									20	0.341	51.4		20	0.507	56.2		20	-0.724	46.4
23									21	0.438	52.6		21	0.666	58.0		21	-0.665	47.0
24									22	0.536	53.8		22	0.829	59.9		22	-0.607	47.7
25									23	0.637	55.1		23	0.997	61.9		23	-0.551	48.3

Therefore, the 0-100 logit score is 56.2 in this case. This is the GHS domain final score. (Range of all domains is 0-100)

Recoding Matrix

Original Score	Recoded Score						
	1	2	3	4	5	6	7
1	0	1	2	3	3	4	4
2	0	1	2	3	4	5	6
3	0	1	1	2	2	3	3
4	0	1	2	3	4	5	6
5	0	1	2	2	3	3	3
6	0	0	1	1	1	2	2
7	0	0	0	1	2	2	3
8	0	0	1	1	1	2	2
9	0	0	1	1	1	2	2
10	0	0	1	1	1	2	2
11	0	1	2	3	4	4	5
12	0	1	2	3	4	5	6
13	0	1	2	3	4	5	6
14	0	1	2	3	4	5	6
15	0	1	2	3	4	5	6
16	0	1	2	3	4	4	5
17	0	1	2	2	2	3	3
18	0	1	2	2	2	3	3
19	0	0	1	1	1	1	2
20	0	1	2	2	2	3	4
21	0	1	1	2	2	2	3

aTyr Pharma, Inc.

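### SAP 11.1.3.3 scores the KSQ GHS-Lung as a 0-200 sum of two logit scores, while the Appendix 1 it cites converts the combined raw total once to 0-100; the two rules differ by more than scale.

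*SAP*

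**What the plan says.** SAP 11.1.3.3 lists five KSQ domains and a combined GHS-Lung score. The domains are logit scores from 0 to 100, "except the GHS-Lung score which is the sum of the GHS and Lungs scores and ranges from 0 to 200". The paragraph ends: "See Appendix 1: King's Sarcoidosis Questionnaire (KSQ) scoring information for further details on KSQ scoring".

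Appendix 1, described there as coming directly from the vendor, works one example for the General Health Status (GHS) domain. Each item is recoded, the recoded items are added, and the last step is: "Convert the re-score total into the logit 0-100 scale by using the logit conversion list". Note 1 extends this: "Use the same principle for other domains and combinations of domains". Note 2 treats combined scores as usually unnecessary, but says that "GHS-Lung is best when a single combined score is required rather than individual domain scores". The conversion lists contain a separate GHS L column that maps raw totals 0 to 67 onto 0 to 100.

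SAP 11.1.3 compares each active arm and the combined active arm with placebo on change from baseline for each subscore or total score, in a mixed model for repeated measures, and summarises the questionnaires in both the mITT and EE Sets. No section says which of the two GHS-Lung rules governs.

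**The concern.** One analysed score has two derivations. Section 11.1.3.3 converts each domain and then adds. Appendix 1 adds and then converts. The conversion lists are curved, steep at the ends and flatter in the middle, so the order of the two steps matters. Two programmers, one working from the section and one from the appendix, would produce different values, different changes from baseline and a different ordering of patients from the same responses.

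At stake is one exploratory comparison with placebo in small groups (8 planned patients per active arm, 12 pooled placebo). The score also could not be compared directly with GHS-Lung values derived elsewhere from the vendor's table. Leaving both rules in place allows a choice between them once results are known, which the SAP's status as an a priori plan (section 3.1) is meant to prevent.

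**Working it through.** **Inputs**, all from the SAP Appendix 1 conversion lists and recoding matrix:
- GHS list (raw 0-33): 10 = 38.0, 15 = 47.1, 20 = 56.2, 27 = 70.9, 30 = 80.3, 33 = 100.
- Lung list (raw 0-34): 10 = 38.8, 11 = 40.2, 15 = 45.5, 20 = 51.4, 27 = 61.0, 30 = 68.0, 34 = 100.
- GHS L list (raw 0-67): 30 = 52.4, 38 = 56.9, 40 = 58.1, 42 = 59.3, 67 = 100.

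**The plan's own figures.** The worked example says "Therefore, re-score total is 20" and then "Therefore, the 0-100 logit score is 56.2 in this case". The GHS list at 20 gives 56.2, so the example reproduces. The upper limit of 200 in 11.1.3.3 also reproduces, as 100 + 100. The recoding matrix gives a maximum of 33 for items 1-10 and 34 for items 11-16, and 33 + 34 = 67, the top of the GHS L list. That list is therefore built for the added GHS and Lung raw totals. (That items 11-16 are the Lung items is inferred from this match.)

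**The two rules**, for GHS raw total g and Lung raw total l:
- Section 11.1.3.3: S = GHS[g] + Lung[l], range 0-200.
- Appendix 1: T = GHS L[g + l], range 0-100.

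Halving S puts both on 0-100, so that any remaining gap is not a matter of units.

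| Raw GHS/Lung | S | S/2 | T |
|---|---|---|---|
| 15/15 | 47.1 + 45.5 = 92.6 | 46.3 | 52.4 |
| 20/20 | 56.2 + 51.4 = 107.6 | 53.8 | 58.1 |
| 30/10 | 80.3 + 38.8 = 119.1 | 59.55 | 58.1 |
| 10/30 | 38.0 + 68.0 = 106.0 | 53.0 | 58.1 |
| 15/27 | 47.1 + 61.0 = 108.1 | 54.05 | 59.3 |
| 27/11 | 70.9 + 40.2 = 111.1 | 55.55 | 56.9 |

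**Changes**
- 15/15 to 20/20: S rises by 107.6 - 92.6 = 15.0, which is 7.5 after halving; T rises by 58.1 - 52.4 = 5.7.
- 30/10 against 10/30: equal by table; 119.1 - 106.0 = 13.1 apart by sum, or 6.55 after halving.
- 15/27 to 27/11: S changes by 111.1 - 108.1 = +3.0 (+1.5 after halving); T changes by 56.9 - 59.3 = -2.4. The sign reverses.

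No constant factor links the two rules. From 20/20, four more raw GHS points give +7.7 by sum and +2.4 by table (ratio 3.21). Four more raw Lung points give +5.0 and +2.4 (ratio 2.08).

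**How much this might matter across patients.** The documents give no KSQ distribution, so this part rests on assumed values: raw means at 45-75% of maximum, SD 6, GHS-Lung correlation 0 to 0.7, and a change per domain with mean +1 and SD 3. Simulated under these assumptions, the rank correlation between the two scores is 0.95 to 0.997 and the correlation between their changes is 0.84 to 0.96. Standardised mean changes run from about 0.3 to 0.45 under either rule.

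**The case against.** The strongest reply is that 11.1.3.3 is an explicit exception. It gives the 0-100 range, excludes GHS-Lung by name and states its range, which looks deliberate. Appendix 1 is cited only for further details and is a general vendor package: it also carries tables for combinations that the SAP never analyses, so the presence of a GHS L table does not alone prove that it is the planned rule. This stands as far as intent goes. It does not remove the conflict, because Note 1 extends the re-score-and-convert method to combinations and the SAP nowhere says that its body overrides that note.

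Three stronger readings are tempting, and the documents do not support them:
- A reader might infer that the sum is an unvalidated score and the table the validated one. The SAP says only that the scoring came from the vendor; it reports no validation of either rule.
- A reader might take +15.0 against +5.7 as a nearly threefold difference in effect. Most of that gap is the 0-200 scale. On a common scale it is +7.5 against +5.7, and doubling a score does not change a p-value in the mixed model.
- A reader might cite "Range of all domains is 0-100" as a direct contradiction of the 0-200 range. That remark closes the GHS example and concerns domains, on which 11.1.3.3 agrees. The 0-100 range for GHS-Lung rests on Note 1 and the GHS L table.

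It is also fair that the 30/10 and 10/30 pair and the sign reversal are discordant splits, chosen to show what can happen and not what is typical.

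**Conclusion.** The inconsistency is real and stands in the current SAP text. The two rules give different values, different changes and, for some patients, a different order or direction of change, and rescaling does not reconcile them. That part is table look-up and needs no assumption.

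The consequence is limited. KSQ is exploratory, the SAP plans no formal hypothesis testing and no multiplicity adjustment, and only the GHS-Lung comparison is touched. The five domain scores are analysed in their own right and are unaffected, as are the primary safety analysis and the secondary corticosteroid and immunogenicity analyses. Under the simulated assumptions the two scores rank patients similarly; their changes agree less closely. The documents do not settle which rule was intended. Appendix 1 is the better default because it is the vendor's method, names GHS-Lung and supplies a table built for it. The point should be corrected, but it does not threaten the trial's main conclusions.

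**What to change.** Before unblinding, rewrite the GHS-Lung clause in SAP 11.1.3.3 to follow Appendix 1: add the GHS and Lung re-score totals (0-67), convert the total with the GHS L table to 0-100, and delete the wording on the sum and the 0-200 range. If the sum was deliberate, state that it departs from the vendor scoring, label it as a non-vendor score in tables and listings, and report the GHS L score alongside it.

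The cost is one SAP sentence and one line of derivation code. No extra data are needed, because both rules use the same item responses. Keeping the sum adds one further derived variable and its summaries.

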11.1.3.4. Leicester Cough Questionnaire (LCQ)

The LCQ is a 19-item self-completed quality of life measure of chronic cough. Items on the scale are divided into 3 domains, physical, psychological, and social. Items are scored on a 7-point Likert scale. The individual domain scores are averages of all questions within the domain (ranging 1-7). A total score (range 3 to 21) is also calculated by adding the domain scores together, with higher scores indicating better quality of life. The minimal clinically important difference (MCID) for chronic cough is 1.3. The LCQ is administered on Day 1 and Weeks 4, 8, 12, 16, 20 and 24/Early Termination Visits. The total and 3 domain scores and change from baseline will be summarized by visit and treatment, as well as being listed with domain scores.

If a question is missing, then the corresponding domain score is set to missing, and the total score is also missing.

11.1.3.5. Fatigue Assessment Scale (FAS)

The FAS contains 10 fatigue questions rated from 1=never to 5=always (about everyday). Missing individual scores are not permitted. Scores on questions 4 and 10 should be recoded (1=5, 2=4, 3=3, 4=2, 5=1). Subsequently, the total FAS score can be calculated by summing the scores on all questions (the recoded scores for question 4 and 10). The sum of questions 3 and 6-9 indicates mental fatigue, and the sum of the questions 1, 2, 4, 5 and 10 indicates physical fatigue. The minimal score is 10, and the maximal score is 50. Scores of ≥ 22 are considered to represent substantial fatigue (Drent *et al*, 2012). A change in the FAS score of 4 points is considered to be the MCID. The FAS is administered on Day 1 and Weeks 4, 8, 12, 16, 20 and 24/Early Termination Visits.

The total score, mental fatigue score and physical fatigue score, as well as their change from baseline will be summarized by visit and treatment. A shift table for total score (Substantial fatigue vs. Moderate fatigue or lower) will be produced by visit and treatment. Individual item scores will be listed.

aTyr Pharma, Inc.
Study ATYR1923-C-002 Statistical Analysis Plan
IND#: 133692

FINAL Version 1.0
2021-08-02

11.1.4. Skin Lesions Assessments

Skin lesion assessments are conducted at Screening (Baseline) and Weeks 2, 4, 8, 12, 16, 20.

Skin Physician Global Assessment (SPGA), scored 0 to 10 using visual analogue scale, with 0 being No Disease, and 10 being as severe as it could be. SPGA information will be listed.

The Sarcoidosis Activity and Severity Index (SASI) is an instrument that will be used to evaluate a lesion prospectively identified as the ‘target’ lesion, located anywhere on the body. The Investigator will score the extent of erythema and induration of this lesion, each on a scale ranging from 0 (none) to 4 (very severe). At each instance, erythema, induration and total score (erythema + induration) will be listed. . If either subscore is missing, the total score is set as missing.

All skin lesion assessments will be listed.

11.1.5. Serum and Tissue Biomarkers

The following biomarkers will be summarized for change from baseline and listed by treatment.

- ACE, neopterin, and sIL2R (disease serum biomarkers) collected on Day 1, Weeks 12, 20 and End of Study Visits.
- Extracellular histidyl-tRNA synthetase (HARS), NRP2, and VEGFC (pathway serum biomarkers) collected on Day 1, Weeks 12, 20 and End of Study Visits.
- State of immune cell anergy in peripheral blood mononuclear cells (PBMCs) collected on Day 1, Week 12 and End of Study Visits.
- Histopathology (skin biopsy) at screening and week 12, and only for selected sites.

12. PHARMACOKINETIC (PK) ANALYSES

Full details on all PK analyses will be provided in separate analysis plans.

aTyr Pharma, Inc.
Study ATYR1923-C-002 Statistical Analysis Plan
IND#: 133692

FINAL Version 1.0
2021-08-02

APPENDIX 1: KING'S SARCOIDOSIS QUESTIONNAIRE (KSQ) SCORING INFORMATION

Calculating the logit scores in KSQ as obtained directly from vendor.

Notes

1. Example below is for the General Health Status domain. Use the same principle for other domains and combinations of domains.
2. The most useful scores are the 5 domain scores GHS, Lung, Skin, Eyes and Medications. Combination of domain scores are possible but usually not necessary (GHS-Lung is best when a single combined score is required rather than individual domain scores).
3. If more than 50% of the answer of a given module is missing, then the module score is considered missing. Combined score of multiple modules is then also considered missing.
4. If 50% or fewer of the questions have missing or invalid results, then the missing scores are replaced with module averages in the original score before re-score.

Step 1: Check the raw item responses as completed by the patient

Quality of life-QOL Domain (General health status)

	In the last 2 weeks...	All of the time	Most of the time	A good bit of the time	Some of the time	A little of the time	Hardly any of the time	None of the time
1	I have felt frustrated	1	2	3	4	5	6	7
2	I have had trouble concentrating	1	2	3	4	5	6	7
3	I have lacked motivation	1	2	3	4	5	6	7
4	I have felt tired	1	2	3	4	5	6	7
5	I have felt anxious	1	2	3	4	5	6	7
6	I have felt aches and pains in my muscles/joints	1	2	3	4	5	6	7
7	I have felt embarrassed	1	2	3	4	5	6	7
8	I have worried about my weight	1	2	3	4	5	6	7
9	I have worried about my sarcoidosis	1	2	3	4	5	6	7

aTyr Pharma, Inc.
 Study ATYR1923-C-002 Statistical Analysis Plan
 IND#: 133692

FINAL Version 1.0
 2021-08-02

	In the last 2 weeks...	A huge amount	Considerable amount	A moderate amount	A Modest amount	A small amount	A tiny amount	None at all
10	Tiredness has interfered with my normal social activities such as going out with friends/family	1	2	3	4	5	6	7

Step 2: Convert these raw individual scores into the re-scores using the Recoding Matrix.

For example, as patient responded to item 1 with “4”, look up rescore value in QOL TAB. This score now is converted to “3.” See screenshot below.

	A	B	C	D	E	F	G	H	I	J	K
1	Item	Max Score	Rescored	1	2	3	4	5	6	7	
2	I0001	4	Y	0	1	2	3	3	4	4	
3	I0002	6		0	1	2	3	4	5	6	
4	I0003	3	Y	0	1	1	2	2	3	3	
5	I0004	6		0	1	2	3	4	5	6	
6	I0005	3	Y	0	1	2	2	3	3	3	
7	I0006	2	Y	0	0	1	1	1	2	2	
8	I0007	3	Y	0	0	0	1	2	2	3	
9	I0008	2	Y	0	0	1	1	1	2	2	
10	I0009	2	Y	0	0	1	1	1	2	2	
11	I0010	2	Y	0	0	1	1	1	2	2	
12											
13		33									
14											
15											

Therefore, re-score total is 20.

Step 3: Convert the re-score total into the logit 0-100 scale by using the logit conversion list and looking up the appropriate domain, e.g. GHS.

	G	H	I	J	K	L	M	N	O	P	Q	R	S	T	U	V	W	X	Y
1		EYE				MEDS			LUNG				GHS				GHS L		
2	-3.646	0.0			0	-2.506	0.0		0	-3.817	0.0		0	-4.283	0.0		0	-4.927	0.0
3	-2.803	11.3			1	-1.76	14.5		1	-2.975	10.4		1	-3.491	9.3		1	-3.875	11.6
4	-2.18	19.6			2	-1.13	26.8		2	-2.402	17.5		2	-2.941	15.7		2	-3.201	19.0
5	-1.719	25.8			3	-0.594	37.2		3	-2.012	22.3		3	-2.558	20.2		3	-2.769	23.8
6	-1.333	31.0			4	-0.094	47.0		4	-1.715	26.0		4	-2.256	23.8		4	-2.459	27.2
7	-0.992	35.5			5	0.395	56.5		5	-1.475	29.0		5	-2.002	26.7		5	-2.22	29.9
8	-0.68	39.7			6	0.929	66.9		6	-1.274	31.4		6	-1.778	29.4		6	-2.026	32.0
9	-0.392	43.5			7	1.649	80.9		7	-1.1	33.6		7	-1.576	31.7		7	-1.863	33.8
10	-0.122	47.2			8	2.627	100.0		8	-0.947	35.5		8	-1.389	33.9		8	-1.722	35.4
11	0.137	50.6							9	-0.808	37.2		9	-1.213	36.0		9	-1.598	36.7
12	0.391	54.0							10	-0.681	38.8		10	-1.046	38.0		10	-1.487	38.0
13	0.649	57.5							11	-0.562	40.2		11	-0.884	39.9		11	-1.386	39.1
14	0.922	61.1							12	-0.45	41.6		12	-0.726	41.7		12	-1.294	40.1
15	1.226	65.2							13	-0.343	42.9		13	-0.57	43.5		13	-1.208	41.0
16	1.589	70.1							14	-0.239	44.2		14	-0.416	45.3		14	-1.128	41.9
17	2.062	76.4							15	-0.139	45.5		15	-0.264	47.1		15	-1.052	42.8
18	2.769	85.8							16	-0.04	46.7		16	-0.111	48.9		16	-0.981	43.5
19	3.827	100.0							17	0.056	47.9		17	0.042	50.7		17	-0.912	44.3
20									18	0.151	49.1		18	0.196	52.5		18	-0.847	45.0
21									19	0.246	50.2		19	0.351	54.3		19	-0.784	45.7
22									20	0.341	51.4		20	0.507	56.2		20	-0.724	46.4
23									21	0.438	52.6		21	0.666	58.0		21	-0.665	47.0
24									22	0.536	53.8		22	0.829	59.9		22	-0.607	47.7
25									23	0.637	55.1		23	0.997	61.9		23	-0.551	48.3

Therefore, the 0-100 logit score is 56.2 in this case. This is the GHS domain final score. (Range of all domains is 0-100)

Recoding Matrix

Original Score	Recoded Score						
	1	2	3	4	5	6	7
1	0	1	2	3	3	4	4
2	0	1	2	3	4	5	6
3	0	1	1	2	2	3	3
4	0	1	2	3	4	5	6
5	0	1	2	2	3	3	3
6	0	0	1	1	1	2	2
7	0	0	0	1	2	2	3
8	0	0	1	1	1	2	2
9	0	0	1	1	1	2	2
10	0	0	1	1	1	2	2
11	0	1	2	3	4	4	5
12	0	1	2	3	4	5	6
13	0	1	2	3	4	5	6
14	0	1	2	3	4	5	6
15	0	1	2	3	4	5	6
16	0	1	2	3	4	4	5
17	0	1	2	2	2	3	3
18	0	1	2	2	2	3	3
19	0	0	1	1	1	1	2
20	0	1	2	2	2	3	4
21	0	1	1	2	2	2	3

aTyr Pharma, Inc.
 Study ATYR1923-C-002 Statistical Analysis Plan
 IND#: 133692

FINAL Version 1.0
 2021-08-02

22	0	0	1	1	1	2	2
23	0	0	1	1	1	2	2
24	0	1	2	2	2	2	3
25	0	1	2	2	2	3	3
26	0	0	1	1	1	2	2
27	0	0	1	1	1	2	2
28	0	0	0	1	1	2	3
29	0	0	1	1	1	1	2

Logit Conversion:

GHS	Logit	Lung	Logit	Med	Logit
0	0	0	0	0	0
1	9.3	1	10.4	1	14.5
2	15.7	2	17.5	2	26.8
3	20.2	3	22.3	3	37.2
4	23.8	4	26	4	47
5	26.7	5	29	5	56.5
6	29.4	6	31.4	6	66.9
7	31.7	7	33.6	7	80.9
8	33.9	8	35.5	8	100
9	36	9	37.2		
10	38	10	38.8		
11	39.9	11	40.2		
12	41.7	12	41.6		
13	43.5	13	42.9		
14	45.3	14	44.2		
15	47.1	15	45.5		
16	48.9	16	46.7		
17	50.7	17	47.9		
18	52.5	18	49.1		
19	54.3	19	50.2		
20	56.2	20	51.4		
21	58	21	52.6		
22	59.9	22	53.8		
23	61.9	23	55.1		
24	63.9	24	56.4		
25	66.1	25	57.8		
26	68.4	26	59.3		
27	70.9	27	61		
28	73.6	28	62.9		
29	76.7	29	65.2		
30	80.3	30	68		

aTyr Pharma, Inc.
 Study ATYR1923-C-002 Statistical Analysis Plan
 IND#: 133692

FINAL Version 1.0
 2021-08-02

31	84.7	31	71.7
32	91	32	77.1
33	100	33	85.8
		34	100

Skin	Logit	Eye	Logit	GHS L	Logit
0	0	0	0	0	0
1	13.7	1	11.3	1	11.6
2	25.4	2	19.6	2	19
3	35.4	3	25.8	3	23.8
4	44.7	4	31	4	27.2
5	53.8	5	35.5	5	29.9
6	63.3	6	39.7	6	32
7	73.7	7	43.5	7	33.8
8	86.1	8	47.2	8	35.4
9	100	9	50.6	9	36.7
		10	54	10	38
		11	57.5	11	39.1
		12	61.1	12	40.1
		13	65.2	13	41
		14	70.1	14	41.9
		15	76.4	15	42.8
		16	85.8	16	43.5
		17	100	17	44.3
				18	45
				19	45.7
				20	46.4
				21	47
				22	47.7
				23	48.3
				24	48.9
				25	49.5
				26	50.1
				27	50.7
				28	51.2
				29	51.8
				30	52.4
				31	52.9
				32	53.5
				33	54.1
				34	54.6
				35	55.2
				36	55.8

aTyr Pharma, Inc.
 Study ATYR1923-C-002 Statistical Analysis Plan
 IND#: 133692

FINAL Version 1.0
 2021-08-02

37	56.4
38	56.9
39	57.5
40	58.1
41	58.7
42	59.3
43	59.9
44	60.5
45	61.2
46	61.8
47	62.5
48	63.2
49	63.9
50	64.7
51	65.4
52	66.2
53	67.1
54	68
55	68.9
56	69.9
57	71
58	72.1
59	73.3
60	74.7
61	76.2
62	77.9
63	80
64	82.6
65	86.1
66	91.5
67	100

GHS S	Logit	GHS E	Logit	GHS LS	Logit
0	0	0	0	0	0
1	9	1	9.1	1	8.5
2	15	2	15.3	2	14.1
3	19.2	3	19.5	3	17.9
4	22.3	4	22.8	4	20.6
5	25	5	25.5	5	22.8
6	27.3	6	27.8	6	24.6
7	29.3	7	29.8	7	26.2
8	31.1	8	31.7	8	27.5

aTyr Pharma, Inc.
 Study ATYR1923-C-002 Statistical Analysis Plan
 IND#: 133692

FINAL Version 1.0
 2021-08-02

9	32.8	9	33.4	9	28.7
10	34.3	10	34.9	10	29.8
11	35.8	11	36.4	11	30.7
12	37.1	12	37.7	12	31.6
13	38.4	13	39	13	32.4
14	39.6	14	40.2	14	33.1
15	40.8	15	41.4	15	33.8
16	41.9	16	42.5	16	34.5
17	43	17	43.5	17	35.1
18	44.1	18	44.5	18	35.6
19	45.1	19	45.5	19	36.2
20	46.1	20	46.5	20	36.7
21	47.2	21	47.5	21	37.2
22	48.2	22	48.4	22	37.7
23	49.2	23	49.3	23	38.2
24	50.2	24	50.2	24	38.7
25	51.2	25	51.1	25	39.1
26	52.2	26	52	26	39.5
27	53.2	27	52.9	27	40
28	54.3	28	53.8	28	40.4
29	55.4	29	54.8	29	40.8
30	56.5	30	55.7	30	41.2
31	57.7	31	56.6	31	41.6
32	59	32	57.6	32	42
33	60.4	33	58.6	33	42.4
34	62	34	59.6	34	42.8
35	63.7	35	60.7	35	43.2
36	65.6	36	61.8	36	43.6
37	67.9	37	62.9	37	44
38	70.6	38	64.1	38	44.4
39	74.2	39	65.3	39	44.8
40	79.1	40	66.7	40	45.2
41	87.1	41	68.1	41	45.6
42	100	42	69.6	42	46
		43	71.2	43	46.4
		44	73	44	46.8
		45	75.1	45	47.2
		46	77.6	46	47.7
		47	80.6	47	48.1
		48	84.6	48	48.6
		49	90.7	49	49
		50	100	50	49.5
				51	50
				52	50.5
				53	51

aTyr Pharma, Inc.
 Study ATYR1923-C-002 Statistical Analysis Plan
 IND#: 133692

FINAL Version 1.0
 2021-08-02

54	51.5
55	52.1
56	52.6
57	53.2
58	53.9
59	54.5
60	55.2
61	56
62	56.8
63	57.6
64	58.6
65	59.6
66	60.7
67	61.9
68	63.3
69	64.8
70	66.6
71	68.8
72	71.4
73	74.8
74	79.6
75	87.3
76	100

GSH LM	Logit	GSH SM	Logit	GSH LSM	Logit
0	0	0	0	0	0
1	8.8	1	10.2	1	9
2	14.7	2	17.2	2	15.2
3	18.6	3	22	3	19.5
4	21.7	4	25.6	4	22.6
5	24.1	5	28.3	5	25.1
6	26.2	6	30.7	6	27.1
7	28.1	7	32.7	7	28.8
8	29.7	8	34.6	8	30.2
9	31.1	9	36.2	9	31.5
10	32.5	10	37.8	10	32.7
11	33.7	11	39.2	11	33.7
12	34.9	12	40.5	12	34.7
13	36	13	41.7	13	35.6
14	37	14	42.9	14	36.4

aTyr Pharma, Inc.
Study ATYR1923-C-002 Statistical Analysis Plan
IND#: 133692

FINAL Version 1.0
2021-08-02

15	38	15	43.9	15	37.1
16	38.9	16	44.9	16	37.8
17	39.8	17	45.8	17	38.4
18	40.7	18	46.7	18	39
19	41.6	19	47.6	19	39.6
20	42.4	20	48.4	20	40.1
21	43.2	21	49.1	21	40.6
22	44	22	49.9	22	41.1
23	44.8	23	50.6	23	41.5
24	45.5	24	51.3	24	42
25	46.2	25	51.9	25	42.4
26	47	26	52.6	26	42.8
27	47.7	27	53.3	27	43.2
28	48.4	28	53.9	28	43.6
29	49.1	29	54.6	29	44
30	49.8	30	55.3	30	44.3
31	50.5	31	56	31	44.7
32	51.2	32	56.7	32	45.1
33	51.8	33	57.5	33	45.4
34	52.5	34	58.3	34	45.8
35	53.2	35	59.2	35	46.2
36	53.9	36	60	36	46.5
37	54.6	37	61	37	46.9
38	55.3	38	62	38	47.2
39	56	39	63.1	39	47.6
40	56.7	40	64.2	40	47.9
41	57.4	41	65.5	41	48.3
42	58.2	42	66.9	42	48.7
43	59	43	68.5	43	49
44	59.8	44	70.3	44	49.4
45	60.6	45	72.4	45	49.7
46	61.5	46	75	46	50.1
47	62.5	47	78.4	47	50.5
48	63.5	48	83	48	50.8
49	64.5	49	89.9	49	51.2
50	65.7	50	100	50	51.5
51	66.9			51	51.9
52	68.2			52	52.3
53	69.7			53	52.7
54	71.3			54	53.1
55	73.2			55	53.4
56	75.3			56	53.8
57	77.8			57	54.3
58	81			58	54.7
59	85			59	55.1

aTyr Pharma, Inc.
Study ATYR1923-C-002 Statistical Analysis Plan
IND#: 133692

FINAL Version 1.0
2021-08-02

60 91.1
61 100

60 55.6
61 56.1
62 56.6
63 57.1
64 57.6
65 58.2
66 58.8
67 59.4
68 60.1
69 60.9
70 61.6
71 62.5
72 63.4
73 64.3
74 65.4
75 66.5
76 67.8
77 69.3
78 71
79 73.1
80 75.6
81 78.9
82 83.5
83 90.1
84 100
